## 8.2. Setting

The study population will consist of patients with a diagnosis of hormone receptor-positive/human epidermal growth factor receptor 2-negative mBC who initiated a who initiated PB+FUL and CCI

The USON includes 1,200 affiliated physicians operating in over 470 sites of care across states and treats approximately 1 million US cancer patients annually.

**Figure 1** presents a graphical depiction of the study time periods, which are as follows:

- Study observation period: 01 February 2016 – 30 June 2020.\*
- Study identification period: 01 February 2016 – 31 December 2019.
- Index date: The date of initiation with PB+FUL or CCI during the study identification period. For PB+FUL, the date of the first administration of either drug will be used.
- Baseline: Assessment will be done for the data collected at the closest date prior to index within 30 days of index (in absolute value). Variables to be assessed at baseline are specified in **Table 2**.
- Prior medical history: Patients' available history in the iKnowMed (iKM) EHR will vary based on the length of disease and the time within the USON. The prior medical history period will end the day prior to the index date. Variables to be assessed with prior medical history are specified in **Table 2**.
- Follow-up: Patients will be followed through the end of the study observation period, date of last visit or date of death, whichever occurs first. For analysis, patients will have a potential of at least 6 months of follow-up duration; however, patients will have variable follow-up time periods, depending on their index dates and last contact dates.

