Menopausal type	Chart review	Baseline characteristic	Prior medical history	If patients were menopausal, whether it was natural or induced and, if induced, the method (luteinizing hormone-releasing hormone [LHRH] suppression, surgical, other).
Healthcare setting and provider characteristics				
Practice location	iKM structured data (derived)	Baseline characteristic	Baseline	
The US census region of the USON clinic where the patient received care at the index visit:
 
Midwest: Illinois, Indiana, Michigan, Ohio, Wisconsin, Iowa, Kansas, Minnesota, Missouri, Nebraska, North Dakota and South Dakota
 
Northeast: Connecticut, Maine, Massachusetts, New Hampshire, Rhode Island, Vermont, Pennsylvania, New Jersey and New York
 
South: Delaware, Florida, Georgia, Maryland, North Carolina, South Carolina, Virginia, Washington D.C., West Virginia, Alabama, Kentucky, Mississippi, Tennessee, Arkansas, Louisiana, Oklahoma and Texas
 
West: Arizona, Colorado, Idaho, Montana, Nevada, New Mexico, Utah, Wyoming, California, Oregon and Washington State
 
Missing clinic values will be captured in a "no information" category.
 
Some of the regions may need to be collapsed if there are small sample sizes (e.g., South versus non-South). This determination will be confirmed after reviewing sample sizes and the added value to the study with McKesson's Privacy and Compliance team.

				CCI
Practice size	iKM structured data (derived)	Baseline characteristic	1/1/2018 – 12/31/2018	
The number of patients seen at the USON clinic where the patient receive care for his/her index visit in the year 2018:
 
<50 patients/ year 50-99 patients/year 100-149 patients/year ≥ 150 patients/year

Physician BC patient volume	iKM structured data (derived)	Baseline characteristic	1/1/2018 – 12/31/2018	
The number of BC patients seen by the physician who provided care for the patient's index visit in the year 2018:
 
<10 patients/ year 11-49 patients/year ≥ 50 patients/year

Physician specialty	iKM structured data	Baseline characteristic	Baseline	
Specialty of the physician who provided care for the patient's index visit:
 
Hematology & medical oncology Internal medicine Other

				Not documented

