Menopausal status	iKM structured data + chart review	Baseline characteristic	Baseline	Categorized as documented by physicians: Pre-menopausal Peri-menopausal Post-menopausal No information

PFIZER CONFIDENTIAL

Menopausal type	Chart review	Baseline characteristic	Prior medical history	If patients were menopausal, whether it was natural or induced and, if induced, the method (luteinizing hormone-releasing hormone [LHRH] suppression, surgical, other).
Healthcare setting and provider characteristics				
Practice location	iKM structured data (derived)	Baseline characteristic	Baseline	
The US census region of the USON clinic where the patient received care at the index visit:
 
Midwest: Illinois, Indiana, Michigan, Ohio, Wisconsin, Iowa, Kansas, Minnesota, Missouri, Nebraska, North Dakota and South Dakota
 
Northeast: Connecticut, Maine, Massachusetts, New Hampshire, Rhode Island, Vermont, Pennsylvania, New Jersey and New York
 
South: Delaware, Florida, Georgia, Maryland, North Carolina, South Carolina, Virginia, Washington D.C., West Virginia, Alabama, Kentucky, Mississippi, Tennessee, Arkansas, Louisiana, Oklahoma and Texas
 
West: Arizona, Colorado, Idaho, Montana, Nevada, New Mexico, Utah, Wyoming, California, Oregon and Washington State
 
Missing clinic values will be captured in a "no information" category.
 
Some of the regions may need to be collapsed if there are small sample sizes (e.g., South versus non-South). This determination will be confirmed after reviewing sample sizes and the added value to the study with McKesson's Privacy and Compliance team.

				CCI
Practice size	iKM structured data (derived)	Baseline characteristic	1/1/2018 – 12/31/2018	
The number of patients seen at the USON clinic where the patient receive care for his/her index visit in the year 2018:
 
<50 patients/year
 
50-99 patients/year
 
100-149 patients/year
 
≥150 patients/year

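### Practice-size classes ending at 150 or more patients a year cannot separate clinics in a network averaging about 2,128 per site, and the fixed 2018 window falls after index for index dates before 2018

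*Protocol*

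**What the plan says.** Protocol Section 8.3, Table 2, defines practice size as "The number of patients seen at the USON clinic where the patient receive care for his/her index visit in the year 2018". The classes are under 50, then "50-99 patients/year 100-149 patients/year ≥ 150 patients/year". The row's role is baseline characteristic and its period of measurement is "1/1/2018 – 12/31/2018". SAP Section 5.4, Table 1, repeats the definition ("The number of patients seen at the USON clinic where the patient receive care"), the period and the classes.

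The next row, physician BC patient volume, has the same role and the same 2018 period. It is "The number of BC patients seen by the physician who provided care for the patient's index visit in the year 2018", in classes of under 10, 11–49, and 50 or more.

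Protocol Section 8.2 gives the context: "Study identification period: 01 February 2016 – 31 December 2019". Its general baseline rule is "Assessment will be done for the data collected at the closest date prior to index within 30 days of index (in absolute value", and Section 8.3 lets individual rows state a different period. Section 8.2 also describes the network: "The USON includes 1,200 affiliated physicians operating in over 470 sites of care", treating roughly 1 million cancer patients a year. Provider- and clinic-level characteristics belong to primary objective 1 (Section 7.1). Neither document gives a reason for choosing 2018 or for the class limits.

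**The concern.** There are two separate problems.

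The first is resolution. The practice-size definition counts all patients at the clinic, whereas the row below it is explicitly limited to BC patients. Class limits of 50, 100 and 150 look far too low for oncology clinics of the size that Section 8.2 implies. If almost every study patient lands in the top class, the row cannot describe the clinics in which first-line palbociclib plus fulvestrant was given. Section 8.9.2 says that network practices may differ from other community practices, and practice size is one of the few planned variables that could help a reader judge this.

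The second is timing. A variable called baseline should describe the clinic or physician at or before the start of treatment. With one calendar year for everybody, patients indexed in 2016 or 2017 receive a value taken entirely from later time.

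**Working it through.** The documents give no expected distribution for either variable, so there is no planned figure to reproduce.

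**Resolution of practice size**

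Inputs from Protocol Section 8.2: about 1,000,000 patients a year, and more than 470 sites (470 used).

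1. Mean per site: 1,000,000 / 470 = 2,128. Against the top limit: 2,128 / 150 = 14.2.
2. A mean alone does not fix the share in each class, but a bound that needs no distribution is available. Patients at clinics below 150 are most numerous if every site sees exactly 149: 470 × 149 = 70,030, and 70,030 / 1,000,000 = 7.0%. So at least 93.0% of network patients attend a clinic in the top class.
3. Applied to the final first-line cohort of 317 (Protocol Table 3), assuming that it is spread like the network: 317 × 0.930 = about 295 patients in one class and at most about 22 in the other three together.
4. Looser inputs:

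| Sites | Patients a year | Most that can be below 150 | Least in top class |
|---|---|---|---|
| 470 | 1,000,000 | 7.0% | 93.0% |
| 600 | 1,000,000 | 8.9% | 91.1% |
| 1,000 | 1,000,000 | 14.9% | 85.1% |
| 470 | 750,000 | 9.3% | 90.7% |
| 470 | 500,000 | 14.0% | 86.0% |

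5. Illustration with an assumed lognormal spread of site sizes, mean 2,128 and coefficient of variation CV. Put s² = ln(1 + CV²) and m = ln(2,128) − s²/2. The share of clinics at 150 or more is 1 − Φ((ln 150 − m)/s). The share of patients at such clinics is 1 − Φ((ln 150 − m − s²)/s). For CV from 0.5 to 3, the patient share runs from 100% down to 99.4%, and the clinic share from 100% down to 83.9%.

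**Timing of both variables**

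The index window, 1 February 2016 to 31 December 2019, has 1,430 days.

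| Index date | Days | Share of window | Position of the 2018 period |
|---|---|---|---|
| Before 2018 | 700 | 49.0% | Wholly after index |
| In 2018 | 365 | 25.5% | Straddles index |
| In 2019 | 365 | 25.5% | Wholly before index |

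For an index date of 1 February 2016 the measurement period starts about 23 months and ends about 35 months after index. These are shares of calendar time. They are shares of patients only if accrual was even, and the documents give no accrual by year.

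**The case against.** The strongest defence is that a fixed year is a deliberate and permitted choice. Section 8.3 allows row-specific periods, so a reader who infers a breach of the 30-day baseline rule would be wrong. One common year puts all clinics on the same footing, and clinic size may change slowly. This stands, but the year is unexplained and the baseline label does not fit index dates before 2018.

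A reader might also infer that every index date outside 2018, about 74% of the window, is mistimed. It is not: for 2019 index dates, 2018 is the preceding calendar year. Nor do the documents show that clinics or physicians left, joined or merged and so received wrong volumes. They contain no turnover data, and SAP Table 2 plans to report missing values for these characteristics.

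On resolution, the network figures are approximate, and the study uses only sites with full use of the record system and data open to research. Table 3 shows 5,594 of 12,918 patients (43%) removed for inaccessible data, so the size distribution at the remaining sites is unknown. This limits the precision of the 93%. The looser inputs show that the conclusion does not depend on it closely.

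The class limits might work if BC patients were meant. Table 3 starts from 19,720 patients with hormone receptor-positive, HER2-negative metastatic disease: 19,720 / 470 = about 42 per site over the whole feasibility period. All BC patients would be more than that, but the documents give no count. This is a real possibility, but the definition would then be wrong and would still need correcting.

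**Conclusion.** The point holds, at low severity. As defined, practice size will place at least about 93% of patients in a single open-ended class, and at least about 85% with 1,000 sites or 500,000 patients a year. This rests on the Section 8.2 network figures and on the cohort being spread like the network. The row therefore adds almost nothing to primary objective 1. Separately, both variables are measured wholly after index for 49% of the index window.

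Three stronger readings are not supported. Near-constancy is not shown for physician BC volume, because the documents give nothing on its spread. The bound concerns patients and does not prove that nearly every clinic is in the top class; in the illustration the clinic share falls to 84%. And no outcome result is affected: neither variable is a listed subgroup (Protocol Section 8.2.3, SAP Section 4.4) or a named propensity-score covariate (Protocol Section 8.7.3, SAP Section 7.1), and no Kaplan-Meier endpoint uses them.

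**What to change.** In Protocol Table 2 and SAP Table 1:

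- State which patients practice size counts: all patients, or BC patients only.
- Report practice size as median and range, with classes set from the observed distribution (quartiles, for example) if classes are wanted. New classes alone would leave the question of who is counted unanswered.
- Measure both variables over the 12 months before index. The calendar year of index would not solve the timing problem, since a January index would still take in about 11 months of later data. Alternatively, keep 2018, give the reason, and call it a fixed reference year rather than baseline.
- In the same edit, close the gap in physician volume, where exactly 10 patients fits neither the first nor the second class.

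SAP Table 2 draws provider and clinic characteristics from structured data only, so no chart needs to be reopened. The cost is a re-run query and changed wording in both documents. Structured data collection is marked complete in July 2020 (Protocol Table 1), so a new extraction may be needed if the window changes. A footnote to Protocol Section 8.7 says that a modified SAP leads to a protocol update and resubmission to the review board, so this is best combined with other edits. Clarifying who is counted, changing the summary, and keeping 2018 with a reason and a new label is the cheapest version.

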iKM use at practice location	iKM structured data	Eligibility criteria	Baseline	Patients who are treated at USON sites that utilize the full EHR capacities of iKM for their index visit will be eligible for participation in the study; otherwise, patients will be excluded.
Data accessibility	iKM structured data	Eligibility criteria	Baseline	Patients whose data are accessible for research purposes will be eligible for participation in the study; otherwise, patients will be excluded.
Disease characteristics				
Date of initial BC diagnosis	iKM structured data + chart review	Eligibility criteria, Baseline characteristic	Medical history prior to index	
To assess BC diagnoses that occurred prior to index, patients' available medical history in iKM will be searched. The completeness of this history will vary based on the length of disease and the time within the USON. Records may also be incomplete for patients with an initial BC diagnosis that occurred outside of the USON.
 
Diagnosis of BC will be determined through a review of iKM's discrete diagnosis and histology fields, which are populated during the routine course of care (International Classification of Diseases [ICD] codes will not be used).
 
If no initial diagnosis date is documented, the first recorded diagnosis date in iKM will be used. This date will be used in calculations, not reported separately.
 
Patients without a recorded diagnosis of BC will be excluded from the study.

Date of mBC disease diagnosis	iKM structured data + chart review	Eligibility criteria, Baseline characteristic	Medical history prior to index	
Date of first recorded diagnosis of metastatic disease within the EHR. Patients will be qualified initially based on the date identified in the structured data; this will be confirmed during chart review among patients selected for chart review. Ultimately, the primary source will be the chart if available.
 
Patients without recorded evidence of metastatic disease will be excluded from the study.
 
Structured data will confirm the patient as metastatic and as available, indicate the earliest associated date of any of these criteria:
 
 
1) Stage IV disease
 
2) Tumor, Node, Metastasis (TNM) stage with M value of 1
 
3) Record of location of metastatic disease
 
4) Current or prior disease status containing reference to metastatic disease
 

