Time since initial BC diagnosis	iKM structured data + chart review (derived)	Baseline characteristic	Medical history prior to index	The duration of time, in weeks, between the date of BC diagnosis and presentation of metastatic disease will be calculated for each patient and summarized as the mean ( $\pm$ SD) and median (range) of values. The number of patients with available data will be reported.

				Date of BC diagnosis and presentation of metastatic disease will be determined as defined above.
Time since mBC diagnosis	iKM structured data + chart review (derived)	Baseline characteristic	Medical history prior to index	The duration of time, in weeks, between the index date and presentation of metastatic disease will be calculated for each patient and summarized as the mean ( $\pm$ SD) and median (range) of values. The number of patients with available data will be reported. Presentation of metastatic disease will be determined as defined above.
Distant metastatic site(s)	iKM structured data + chart review	Baseline characteristic	Medical history prior to index	Baseline metastatic location(s) will be identified and categorized as: Bone (single) Bone (multiple) Brain Liver (single) Liver (multiple) Lung (single) Lung (bilateral) Lung (pleural effusion) Lymph nodes (regional) Lymph nodes (distant) Ovary Other No information Note, "no information" can indicate that metastases were not documented in the chart, not necessarily that patients did not have metastases.
Endocrine sensitivity at 12 months	iKM structured data	Baseline characteristic	Baseline	Patients who experienced relapse more than 12 months of completing adjuvant endocrine therapy will be considered to be endocrine sensitive; those who relapse in less than 12 months, endocrine resistant.
Endocrine sensitivity at 24 months	iKM structured data	Baseline characteristic	Baseline	Patients who experienced relapse more than 24 months of completing adjuvant endocrine therapy will be considered to be endocrine sensitive; those who relapse in less than 24 months, endocrine resistant.
Visceral/non-visceral status	iKM structured data + chart review (derived)	Baseline characteristic	Medical history prior to index	Categorized as: Visceral (asymptomatic or symptomatic*) Adrenal gland Bronchus Cervix Esophagus Gastrointestinal tract Genital organ Intestinal tract Kidney Large intestine Liver Lung Mediastinum Omentum Other respiratory organ Other urinary organ Ovary Pancreas

PFIZER CONFIDENTIAL

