				
Pericardium Peritoneum Pleura Rectum Retroperitoneum Small intestine Spleen
 
Non-visceral
 
Brain Breast Cervical nodes Chest wall Eye Ipsilateral supraclavicular lymph node Leptomeninges Other parts of nervous system Skin Spinal cord
 
Bone only
 
Bone Bone marrow Skull
 
Other
 
No information
 
The above list will be confirmed or updated after chart review is complete
 
*Asymptomatic visceral disease will be captured by chart review for patients who have explicit documentation of symptoms in the EHR records. All others will be assumed to be asymptomatic.

Count of metastatic site(s)	iKM structured data + chart review (derived)	Baseline characteristic	Medical history prior to index	
The total count of metastatic site(s) at index:
 
No documentation 1 2 3 4+
 
Note, “no documentation” can indicates that metastases were not documented in the chart, not necessarily that patients did not have metastases.

Stage at diagnosis	iKM structured data	Baseline characteristic	Medical history prior to index	
Categorized as:
 
Stage 0 Stage IA Stage IB Stage IIA Stage IIB Stage IIIA Stage IIIB Stage IIIC Stage IV No information

Eastern Cooperative Oncology Group	iKM structured data	Baseline characteristic	Up to 90 days prior to index	The ECOG performance status score is a rating of a patient's disease status, daily living activities and quality of life, with low

PFIZER CONFIDENTIAL

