6 HANDLING OF MISSING VALUES

In the case of missing observations, the number and percentage of missing values will be reported. No imputation for missing values will be performed.

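### Two baseline rows turn absent documentation into a value, although SAP Section 6 rules out imputation, and the missingness is hidden

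*Protocol*

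**What the plan says.** **Symptom status.** The *Visceral/non-visceral status* row (Protocol Section 8.3, Table 2; SAP Section 5.4, Table 1) splits visceral disease into asymptomatic and symptomatic. Its footnote reads "Asymptomatic visceral disease will be captured by chart review for patients who have explicit documentation of symptoms in the EHR records", followed by "All others will be assumed to be asymptomatic".

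**Initial diagnosis date.** The *Date of initial BC diagnosis* row in both tables says "If no initial diagnosis date is documented, the first recorded diagnosis date in iKM will be used" and adds "This date will be used in calculations, not reported separately". It also warns: "Records may also be incomplete for patients with an initial BC diagnosis that occurred outside of the USON". The date feeds *Time since initial BC diagnosis*: "The duration of time, in weeks, between the date of BC diagnosis and presentation of metastatic disease will be calculated for each patient". That row promises the number of patients with available data.

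**Missing data.** SAP Section 6 says "In the case of missing observations, the number and percentage of missing values will be reported" and then "No imputation for missing values will be performed". SAP Table 2 (Section 7.2.2) likewise lists missing values as reported for baseline characteristics. Protocol Section 8.7.2 differs: where much is missing or illogical, it leaves including, excluding or imputing a variable to a later sponsor decision.

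**The concern.** Both rules assign a value where the record is silent, and SAP Section 6 exempts neither. A visceral patient whose chart says nothing about symptoms is counted together with one documented as symptom-free. A patient whose true first diagnosis date is unknown gets a date that may be late, and the protocol itself expects gaps for diagnoses made outside the network.

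Describing baseline characteristics is the first primary objective (Protocol Section 7.1), so an error in description falls on the objective itself. A reader of the final tables could not detect it. Symptom status has no category for missing documentation, and the available-data count for the interval would include patients whose date was substituted.

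**Working it through.** **1. The texts side by side**

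| Item | Row rule (Protocol Table 2, SAP Table 1) | SAP Section 6 | Protocol Section 8.7.2 |
|---|---|---|---|
| Symptoms not documented | Class as asymptomatic | Count as missing, do not impute | Sponsor decides later if much is missing |
| Initial diagnosis date not documented | Use first recorded iKM date | Count as missing, do not impute | Sponsor decides later if much is missing |

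An analyst cannot follow all three columns as they stand. Neighbouring rows (metastatic sites, stage, ECOG, BRCA, ESR1) keep a no-information category. The visceral row has one for site but none for symptom status.

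**2. The symptom footnote read literally.** Its first sentence assigns asymptomatic disease to patients with documented symptoms, and its second assigns everyone else to asymptomatic. Taken literally, nobody can be symptomatic. The first sentence is evidently inverted. The rest of this check takes the likely intent: documented symptoms mean symptomatic, all others asymptomatic.

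**3. Direction**
- *Symptoms.* The default adds patients only to the asymptomatic class, so it overstates that share unless symptoms from other causes are wrongly recorded as symptomatic visceral disease.
- *Interval.* For a given metastatic date, a first iKM date later than the true diagnosis shortens the interval. The metastatic date is also a first-recorded date within the EHR, and its late recording lengthens the interval. The net error therefore tends towards shortening but is not bound to it.

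**4. Size, as illustration only.** The documents give no visceral share, no symptom documentation rate and no rate of undocumented dates. The only figure taken from them is the 317 first-line PB+FUL patients (Protocol Table 3). All else is assumed.

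*Symptoms.* Reported symptomatic share = p × s, where p is the true share and s the share of charts with a symptom statement, assumed unrelated to true status and without false positives.
- With visceral disease in 40% to 60% of 317, there are 127 to 190 visceral patients.
- At p = 40% and s = 70%: 0.40 × 0.70 = 28%, which is 12 points too low. Patients moved to asymptomatic: 127 × 0.40 × 0.30 ≈ 15 to 190 × 0.40 × 0.30 ≈ 23. Silent charts: 127 × 0.30 ≈ 38 to 190 × 0.30 = 57.
- Smallest error, p = 20% and s = 90%: 18%, 2 points too low. Largest, p = 60% and s = 50%: 30%, 30 points too low.
- At s = 100% the error is zero.

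*Interval.* Reported mean = (1 − m) × T + m × r × T, where T is the true mean, m the share of substituted dates and r the share of the true interval kept. Substituted patients are assumed to share the same true mean, and the metastatic date is taken as correct. With T = 260 weeks:
- m = 5%, r = 0.5: 0.95 × 260 + 0.05 × 0.5 × 260 = 253.5 weeks.
- m = 20%, r = 0: 0.80 × 260 = 208 weeks.
- At m = 0 the error is zero.

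*Available-data count.* If every patient has some iKM diagnosis date, the count reads 317. Without substituted dates it would be 317 × 0.95 ≈ 301 at m = 5%, or 317 × 0.80 ≈ 254 at m = 20%.

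**The case against.** The strongest reply is that these are pre-specified operational definitions, worded identically in both documents, and that SAP Section 6 governs only what is still missing after they apply. That reading is possible, but Section 6 does not say so, and it would still leave the substitutions uncounted.

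Chart review is a better answer on size. The 317 patients come out of the chart-review attrition. Abstractors read the whole medical record (Protocol Section 8.4), and chart data supersede structured data (Section 8.3). The date fallback therefore applies only when chart and structured fields are both silent. This stands, and it may make the date error small. It does not help the symptom row, where the default is applied to the chart review itself.

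The reach is also narrow: one sub-label and one interval. Neither is a listed stratum, an endpoint or one of the example propensity covariates, and no hypothesis is tested for the primary objectives (SAP Section 3.1).

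Three stronger readings are tempting, and the documents support none of them:
- *That referred patients get an interval of about zero weeks.* This is the worst case. A patient who joined the network with early disease keeps part of the interval, and the first date recorded in iKM may mean the earliest diagnosis date held there.
- *That the de novo versus relapsed strata are contaminated.* Neither document derives that status from these dates. Stage at diagnosis, prior adjuvant treatment and disease-free interval are separate variables. The effect arises only if the status is in fact derived from the two diagnosis dates.
- *That the baseline tables will be wrong.* With complete documentation neither rule changes anything.

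**Conclusion.** The point holds as a conflict between the two rows and SAP Section 6, with a known tendency and hidden missingness. Where records are incomplete, the asymptomatic share tends to be overstated and the diagnosis-to-metastasis interval shortened, and the planned tables would not show how often a default was used.

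The size cannot be derived from the documents. The ranges of 2 to 30 points for symptoms, and of 208 to 253.5 weeks against an assumed 260, rest wholly on the stated assumptions. The visceral versus non-visceral and bone-only strata are untouched. The inverted footnote needs correcting whatever the size, because it cannot be applied as written. The change is worth making because it is cheap and the affected items belong to a primary objective.

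**What to change.** Make these changes in both Protocol Table 2 and SAP Table 1:

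1. **Symptom status.** Correct the inverted sentence. Replace the default with two classes for visceral disease: symptoms documented, and symptoms not documented. Add a documented-asymptomatic class only if the eCRF captured it. Chart review ended in December 2020, and neither document shows that silent charts were separated from documented symptom-free ones, so a three-class split could otherwise need re-abstraction.
2. **Initial diagnosis date.** Flag and count patients with a substituted date, leave them out of the available-data count, and show *Time since initial BC diagnosis* with and without them. Showing both matters because dropping them outright could under-represent patients referred from outside the network.
3. **Missing-data text.** Align SAP Section 6 and Protocol Section 8.7.2 with each other and with the two rows, naming any default that is kept as an exception.

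The cost is wording in two rows and two sections, a flag in the dataset, a visible not-documented share and one extra table line.
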